4 DATA COLLECTION

4.1 Baseline

The baseline survey will collect data by questionnaire on self-reported medical history (hypertension, diabetes, stroke, heart failure, angina, heart attack), family history of heart problems and stroke, smoking, most recent use of primary care clinics in the last 12 months, and their preferred clinic. Participants' blood pressure, total cholesterol, random blood glucose (using an Omron automatic blood pressure machine [model M6W]) and waist circumference will be measured by trained field staff. The sample for the survey will be drawn from the Agincourt HDSS census database. In addition to the information collected from the participants, the following personal and household level information will be drawn from the census database: sex, household, date of birth, marital status, education, employment status, household asset score and nationality of origin.

4.2 Follow up

The follow-up survey will use a different sample, which will be selected using the same age/sex distribution. The data collection will be the same as that listed above for the baseline survey.

4.3 Timing of Data collection

The baseline survey took place September – November 2013, following which the intervention started in February 2014 and last for 21 months. The follow-up survey took place September to November 2015.

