3 STUDY METHODS

3.1 Overall Study Design and Plan

We will conduct a cluster-randomised trial in tandem with a detailed realist evaluation. drawing on global experience of evaluating complex interventions^{1,2}. The units of randomisation will be health facilities and their surrounding catchment populations. We propose to randomise eight clinics, four of which will receive the intervention. To achieve our primary outcome, we aim to both increase the proportion of the population under active management for their hypertension and reduce the level of blood pressure in those patients already receiving care. For this reason, the outcome of the trial will be measured at population level, and we estimate that the trial has a power of above 80% to detect an 11% to 13% reduction in the proportion of the population at moderate or greater cardiovascular risk as a result of their blood pressure and other risk factors. Realist evaluation will provide data on adaption of the intervention to the context, individual and organizational processes of change as well as contextual factors that influence outcomes³. We are collecting data at two cross-sectional points 24 months apart: baseline (when intervention is introduced) and at the end of intervention at each clinic to provide data on the sustainability of the intervention. The detailed study methods are described in the following sections.

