5.2 Population Surveys

Two population surveys were carried out (one before the intervention starts and one after it finishes) to estimate the primary outcome of the trial. In each survey, a random sample of 5000 people aged over 18 years were selected from census records, to allow for 20% attrition, so that at least 4000 individuals were included in each survey, contributing approximately 500 people in each of the 8 clusters. From previous experience in this research setting, we expect good participation (~80%). The sample was disproportionately stratified to ensure adequate representation of males and older people. This is necessary because the population pyramid is heavily weighted to younger people and there are fewer men than women amongst older adults due to labour migration.

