5.8 Description of clinic link data

The clinic link data will provide information on attendance at any one of the eight trial clinics over a period of around 18 months by residents of the Agincourt research census site. Consenting individuals attending a clinic are identified in real time on the census data base (using fuzzy matching) by trained data clerks posted in all the clinics. Information about all clinic attendances of identified individuals, including diagnosis and medication prescribed, is recorded. These linked data will enable us to compute by clinic:

- The proportion of people in the population recorded as having attended each clinic in the last year
- Proportion of appointments kept during the study period by those individuals with a diagnosis of hypertension.

The clinic link data also provide the potential to describe socio-demographic differences between those who attend and those who do not attend the clinics – an investigation of association with secondary outcomes (bullet points above) using the logistic regression models, taking into account the clustering in the data.

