5.12 Baseline comparability of randomized groups

Once the database is complete with data from both population surveys entered, we will compare the respondents' characteristics by randomised group and by individual clinic to assess the comparability of the groups. We want to ensure that individuals in the control and intervention clusters are similar by describing their socio-demographic factors; these will be described for both the baseline and the follow-up survey. If similar, this will strengthen our findings to the extent that other factors constant, we can attribute differences after 24 months to the intervention strategies in place. We will also compare with the intervention and control group those individuals surveyed who did not attend a participating clinic – we expect these numbers to be small.

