6 ANALYSIS OF PRIMARY OUTCOME

6.1 Definition of outcome measure

The primary outcome will be the change in the percentage of people in the population who have elevated blood pressure that is combined with other factors resulting in a risk profile that indicates moderate or greater added risk of cardiovascular disease. as indicated by the shaded cells in Table 2. This includes individuals with either: a systolic blood pressure of 160 and above, diastolic of 100 and above, systolic blood pressure of 140-159 plus one or more risk factors, or diastolic blood pressure 90-99 plus one or more risk factors. These data will be obtained from two population surveys (one before the start of the trial and one after the trial ends).

Table 2. Modified South African Guideline: Stratification of cardiovascular risk in patients with hypertension (defined as SBP>139 or DBP>89)

Blood pressure (mmHg)	Presence of risk factors or other conditions						
	No risk factors	One or two risk factors	Three or more risk factors or diabetes	Associated clinical conditions			
SBP 140 -159 or DBP 90-99	Low Added Risk	Moderate Added Risk	High Added Risk	Very High Added Risk			
SBP 160 -179 or DBP 100-109	Moderate Added Risk	Moderate Added Risk	High Added Risk	Very High Added Risk			
SBP 180 + or DBP 110+	High Added Risk	Very High Added Risk	Very High Added Risk	Very High Added Risk			

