cardiovascul	proportion(n))		proportion	1(11)		statistic assessing
ar risk							difference
	Baseline	End	Within	Baseline	End	Within	between cluster
	Prop (n)	Prop (n)	cluster	Prop (n)	Prop (n)	cluster	change and p-
			change			change	value
			and p-			and p-	Value
			value			value	
No or low							
risk							
No risk							
Low risk							
Moderate or							
higher risk							
Moderate							
risk							
High risk							
Very high							
risk							

Repeat for men and women

	Control proportion((n)		Intervention proportion		Statistical Test statistic assessing	
	Baseline Prop (n)	End Prop (n)	Within cluster change and p- value	Baseline Prop (n)	End Prop (n)	Within cluster change and p- value	difference between cluster change and p- value
People with moderate or higher risk***							
Undiagnosed hypertension							
Self-reported blood pressure measured							
Self-reported using medication for hypertension							
Self-reported attended a clinic in the last year.							

Table 10: Changes in hypertension risk, blood pressure, medication and attendance within clusters

Variable		Cont	rol clinic	S		Interv	Intervention clinics		
		1	2	3	4	1	2	3	4
Total number of	of visits								
Number of pat	ients								
Sex	Male								
	Female								
Age	Mean age								
Patient	Visit with 3								
attendance	days of								
(Proportion	appointment								
of visits	Visit NOT								
attended	within 3 days								
within 3 or	of								
less days of	appointment								
appointment	No								
date)	appointment								
Given full set	Yes								
of medication	No								

Table 11: Clinic link record of number of visits by sex, age, patient attendance and availability of medication over 4 time periods (each 5 months long)

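### On the SAP's own dates, most of the follow-up survey was taken while the intervention was still running, so it is not the post-intervention survey that 5.2 and 6.1 describe and cannot show sustainability

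*SAP*

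**What the plan says.** The SAP places the follow-up survey relative to the intervention in several ways.

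- **4.3** gives the calendar. Baseline fieldwork ran over three months of 2013, September to November. For what came next, the section has: "following which the intervention started in February 2014 and last for 21 months. The follow-up survey took place September to November 2015".
- **5.2** describes the two surveys as "one before the intervention starts and one after it finishes".
- **6.1**, which defines the primary outcome, has "one before the start of the trial and one after the trial ends". Section 2.2.1 likewise sets the surveys before and after the intervention.
- **3.1** gives the survey spacing as 24 months, equates baseline with the introduction of the intervention, and puts the second survey "at the end of intervention at each clinic to provide data on the sustainability of the intervention".
- **5.12** says that, if the groups are similar, "we can attribute differences after 24 months to the intervention strategies in place".

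The clinic link data have their own time frame. Section 4.5 has visits recorded during the intervention period. Section 5.8 describes "attendance at any one of the eight trial clinics over a period of around 18 months". The title of dummy Table 11 in Appendix B refers to "availability of medication over 4 time periods (each 5 months long"). Section 6.5 mentions 21 months of follow-up.

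**The concern.** The time point is part of the primary outcome's definition. A survey taken after a service intervention has stopped asks whether its effect persists. A survey taken while lay health workers are still in the clinics asks what the effect is during delivery. Sections 5.2 and 6.1 describe the first kind, and the dates in 4.3 describe mostly the second.

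Two statements in the plan depend on which it is. The sustainability clause in 3.1 needs measurements some time after the intervention ends. The attribution sentence in 5.12 could be taken to mean 24 months of intervention, when 4.3 gives 21. If the wording stands, a report could follow it and present an effect measured largely during delivery as one that had been sustained afterwards.

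**Working it through.** **Inputs, all from the SAP.** Baseline survey September to November 2013; intervention start February 2014, day not given; duration 21 months; follow-up survey September to November 2015 (all 4.3). Survey spacing 24 months (3.1). Randomisation 22 January 2014 (Appendix A).

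**Assumption.** Only months are given, so the follow-up window is taken as 1 September to 30 November 2015: 30 + 31 + 30 = 91 days. The February start day is varied over its whole range.

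**The plan's own figure.** September 2013 to September 2015 is 24 months, and November 2013 to November 2015 is 24 months. The stated survey spacing reproduces exactly.

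**End of intervention and overlap.** The last intervention day is the start date plus 21 months, less one day. Overlap is the number of days from 1 September 2015 to that day, inclusive.

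| Start | Last day | Survey days inside the intervention | Share of 91 | Survey days after |
|---|---|---|---|---|
| 1 Feb 2014 | 31 Oct 2015 | 30 + 31 = 61 | 67% | 30 |
| 14 Feb 2014 | 13 Nov 2015 | 61 + 13 = 74 | 81% | 17 |
| 28 Feb 2014 | 27 Nov 2015 | 61 + 27 = 88 | 97% | 3 |

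These are shares of the window in days. They are shares of respondents only if interviews were spread evenly over the three months, which the SAP does not say.

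**Time since start at interview.** On 1 September 2015 this is 19.0 months for a 1 February start and 18.1 months for a 28 February start. Exposure is capped at 21 months by the stated duration, so it is about 18 to 21 months at interview.

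**Baseline against introduction.** From the last baseline day (30 November 2013) to the earliest start (1 February 2014) is 2.1 months. From the first baseline day (1 September 2013) to the latest start (28 February 2014) is 5.9 months. Baseline fieldwork therefore preceded the start by about 2 to 6 months, so the description in 3.1 of baseline as the moment of introduction is also loose.

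**Start by clinic.** February 2014 begins 10 days after randomisation and ends 37 days after it. The meeting notes in Appendix A list recruitment, clinic workshops and training of lay health workers as steps still to come. This does not show that delivery started late, but it is a reason to state the actual start for each clinic.

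**Clinic link periods.** Table 11 needs 4 × 5 = 20 months. If the data cover 18 months, three full periods use 15 and the fourth holds 18 − 15 = 3 of its 5 months. Because 5.8 gives 18 only as an approximation, the shortfall is illustrative.

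**The case against.** The strongest reply is that the SAP already has the timing about right in other places. Section 3.1 puts the survey at the end of the intervention, 3.4 has the field team trained as the intervention nears its close, Appendix B labels the columns as endpoint or end of intervention, and 4.3 gives the dates openly. On this view the defect is loose wording in a few places. Measuring in the closing months is a legitimate choice, and neither the test, the power calculation nor the analysis population depends on it. Sustainability is not an objective or an outcome, and no analysis in sections 6 or 7 tests it.

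Much of this stands. The conflict is between sections of the SAP, and the fix is to reconcile them. It does not remove the point, because one of the conflicting statements is in the primary outcome definition and the sustainability clause claims something the design cannot deliver.

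Three stronger readings are tempting, and the document does not support them:

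- **That the survey fell almost wholly inside the intervention.** This holds only for a late-February start. An early-February start leaves 30 of 91 days afterwards.
- **That the SAP states a 24-month exposure.** It does not. It gives 24 months as the survey spacing, correctly, and 21 months for the intervention. A 24-month exposure is at most implied by 3.1 and 5.12.
- **That Table 11 would show a large artificial drop in retention.** A short period lowers raw visit and patient counts. It does not by itself lower the proportion of appointments kept, which is the retention outcome.

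**Conclusion.** The point holds for every start date in February 2014. Between two thirds and nearly all of the follow-up survey window (61 to 88 of 91 days) precedes the end of the intervention, contrary to 5.2, 6.1 and 2.2.1. At most 30 days of fieldwork follow it and no later survey is planned, so the sustainability statement in 3.1 has no data behind it. The primary result should be read as an effect at about 18 to 21 months, mostly under active intervention.

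A reader might infer that the primary comparison is biased. The document does not support that: it gives a single follow-up window, with no difference by arm, so the contrast between arms stands. What narrows is the description of what was estimated. The Table 11 mismatch is minor and affects descriptive counts only.

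The result rests on the months in 4.3, on a window running from the first to the last day of those months, and on a 21-month duration that applies to all intervention clinics.

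**What to change.** 1. In 4.3, state the actual start and end dates of the intervention, by clinic if they differ.
2. Bring 2.2.1, 3.1, 5.2 and 6.1 into line with those dates by describing the follow-up survey as taken in the closing months of the intervention.
3. In 3.1, delete the sustainability statement or redefine it as something this survey can show. Correct the description of baseline as coinciding with introduction.
4. In 5.12, label the 24 months as the interval between surveys, so that it is not taken as length of exposure.
5. Report time from intervention start to interview, by clinic, in one short table.
6. As a minor point, set the Table 11 periods to the actual clinic link recording window, or report counts per month, so that a short period is not mistaken for a trend.

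The cost is wording plus one table from survey and intervention dates that should already be held. No new data or change of test is needed. The stated conclusion becomes narrower, since no claim can be made about persistence after the intervention ends.

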4.4 Assigning population survey participants to clusters

The survey asks two questions, one on usual clinic and the other on last clinic used. For the main analyses, the "usual clinic" variable was be used to assign individuals in the survey to a cluster. Some individuals had a usual clinic that was not participating in the study. These individuals will be excluded from the analyses but their results will be briefly described.

4.5 Clinic link data

During the intervention period, a study data clerk asked every chronic patient arriving at both control and intervention clinics, for consent to collect data from their clinical file and to link it to their census record. Following consent, all visits for that patient were then recorded.

5 GENERAL ISSUES FOR STATISTICAL ANALYSIS

5.1 Blinding of the Statistical Analysis

Clinic identifiers were encrypted in the dataset, so that the primary analysis is carried out blinded to which group of clinics are the intervention clinics.

5.2 Population Surveys

Two population surveys were carried out (one before the intervention starts and one after it finishes) to estimate the primary outcome of the trial. In each survey, a random sample of 5000 people aged over 18 years were selected from census records, to allow for 20% attrition, so that at least 4000 individuals were included in each survey, contributing approximately 500 people in each of the 8 clusters. From previous experience in this research setting, we expect good participation (~80%). The sample was disproportionately stratified to ensure adequate representation of males and older people. This is necessary because the population pyramid is heavily weighted to younger people and there are fewer men than women amongst older adults due to labour migration.

5.2.1 Intent-to-treat and Per protocol population

We will conduct an intention-to-treat analysis with respect to clinic. Since we were not recruiting individuals and collecting data from cross-sectional surveys the concept of intention-to-treat does not apply to these individuals in the usual way. Individuals were asked to specify their usual clinic and the last clinic that they attended. For the primary analysis they will be analysed in the clinic they specify as "usual", assuming therefore that the intention was that they received the intervention. Those individuals who specify a "usual" clinic outside the 8 intervention and control clinics will not be included in this analysis. We will undertake a sensitivity with individuals analysed in the "last" clinic that they attended – see also section 6.5.

5.3 Database

5.3.1 Data quality

Quality control process started in the field. Fieldworkers check their own forms for completeness. Thereafter, the Team Supervisors re-check the forms and return those not complete to the field workers for completion. Forms designated as complete by the Team Supervisors are then passed to a Quality Checker who further checks them for completeness and consistency. All forms identified with problems by the Quality Checker are returned to the Project Site Manager. The Project Site Manager discusses the problems with the field teams and gives the forms back to the Fieldworkers to correct. After correction, the forms are sent again to the Quality Checker. Forms that satisfactorily pass the Quality Checker's checks are afterwards sent for data entry.

The data is being entered into a Microsoft SQL server relational database through a user interface written in Visual Basic.net. Two Data Capturers independently enter the data from each form. On entry, the data from each form undergoes validation and consistency checks that are built into the data entry software. Forms whose data fail the checks are returned to the field teams for correction. After data entry, the Quality Checker runs a program that compares the first and second entry records and corrects discrepancies between them. Corrected records and records that had no mistakes are copied into a verified entry record in the database.

Data are entered while fieldwork is still in progress so that mistakes could be rectified immediately. All the forms had a unique barcode identifier that is used to tracking the movement of the forms at each point of the quality control, data entry and data verification processes.

5.3.2 Database freeze

The data base will be frozen once all the data from both surveys have been entered and all validity checks have been completed. Date of database freeze to be confirmed

5.4 Analysis software

All the statistical analysis will be done using Stata versions 13 and 14, from within which "do" (STATA program) files for data management, preliminary analysis and main analysis will be done with comments for ease of follow-ups. Further, log files will be used to keep track of output data.

5.5 Methods for withdrawals, loss to follow-up and Missing Data

We will not have withdrawals nor loss to follow-up since this is a survey cross-sectional design. However, participants selected for the sample may not be present when we visit the household the first time, in which case we will carry out up to two more call backs. In the case where field call backs and tracing have not been successful to ensure all key data have been collected, multiple imputation methods will be used to generate outcomes. For example, blood pressure level might be missing for some cases. We will conduct a complete case analysis and also an analysis where missing blood pressure levels are imputed (imputed analysis) and compare whether there are apparent variations in the results obtained. The same applies for other key variables like self-reported hypertension.

Multiple imputation methods for cluster randomised trials with few clusters are not well developed, although this is a growing research field. A systematic review done recently showed none of the studies reviewed had a multiple imputation procedure that handled clustering and very few techniques also used these in regression models that truly adjusted for the clustering effect⁷. We intend to implement some of these procedures in our analysis as part of sensitivity analysis, but the main analysis will be based on the complete cases.

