The second secondary outcome checks for **change in the proportion of the population reporting they had had their blood pressure measured**. This will be derived from Question 4 – "Have you ever had your blood pressure measured by a *doctor, nurse or other health workers?*" The third secondary objective is on **change in the proportion of the population reporting that they are using medication for hypertension.** Derived from Question 3 – "Have you received any drugs for high blood pressure prescribed by a doctor, nurse or other health worker in the last two weeks?. These two are direct variables from the questionnaire and do not need any further computation. For the primary analysis of this outcome, only those who name specific drugs will be categorized as being prescribed drugs for high blood pressure.

The fourth is change in the proportion of the population at different levels of bloodpressure-related cardiovascular risk by age group and sex. In this case we will also need **blood-pressure-related cardiovascular risk** divided into the different levels of no added risk, low added risk, moderate added risk and high added risk (see Table 2).

The secondary objectives under section 2.2.2, e and f (restated below) do not need any additional computations, and will be derived from clinic link data. These two outcomes are:

- e) Change in the proportion of people in the population recorded as having attended a clinic in the last year.
- f) Retention in care of people with diagnosed hypertension defined by the proportion of appointments kept during the study period.

Note that the clinic link data will provide information on the proportion of people recorded as having attended a clinic in the last year, rather than, as originally stated, reporting they had attended.

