7 ANALYSIS OF SECONDARY OUTCOMES

7.1 Secondary analysis

Secondary outcomes will be analyzed as described above for the primary outcome. They will include: proportion of population in each cluster screened (data from the population survey), adherent to medication and retained in care (from records of clinic activity). Adherence will be defined by using the records of pharmacy refills. The secondary objectives will investigate changes in proportions independently and dependently. The independent tests for proportions (Pearson's Chi-Square test) will be used for assessing between control and intervention/clusters change at the same time point.

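### Secondary outcome f is called retention in care, but as laid out it measures punctuality among attenders and hardly registers patients who leave; the no-loss statement in SAP 5.5 holds only for the surveys

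*SAP*

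**What the plan says.** Sections 2.2.2 and 5.7 give outcome f as "Retention in care of people with diagnosed hypertension defined by the proportion of appointments kept during the study period". Section 5.7 adds that outcomes e and f "do not need any additional computations, and will be derived from clinic link data".

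Those data arise at the clinic. Under section 4.5 a chronic patient enters on arrival and consent: "Following consent, all visits for that patient were then recorded". Section 5.8 says: "Information about all clinic attendances of identified individuals, including diagnosis and medication prescribed, is recorded", and gives the coverage as "over a period of around 18 months". Neither section describes a record for a patient who does not come.

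Section 2.2.2 names Table 11 (Appendix B) as the place where outcome f is reported. Its attendance rows are: visit within 3 days of the appointment, visit not within 3 days, and no appointment. All three are categories of visits made.

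Section 5.5 says of the study as a whole: "We will not have withdrawals nor loss to follow-up since this is a survey cross-sectional design". Section 6.5, by contrast, refers to many appointments over 21 months of follow-up and calls the data longitudinal. It keeps the related missing-data work exploratory and outside the main trial report. The SAP gives no rule for a clinic-link patient who stops attending, dies, moves away or withdraws consent.

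**The concern.** Retention in care asks whether patients are still being seen. A ratio built from visits made cannot answer that, because a patient who leaves for good stops contributing to both numerator and denominator. Someone who attended punctually for a few months and never returned scores perfectly, while someone who stays in care throughout but usually comes more than 3 days late scores badly.

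This is more than missing detail. The definition, the data source and the table are all fixed, and together they give a figure that does not match its label. At stake is one named secondary outcome: the trial could report high retention in both arms whatever the true drop-out, and a real gain in keeping hypertensive patients in care could go unseen.

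**Working it through.** The SAP gives no retention figure, drop-out rate or appointment interval, so there is nothing to reproduce. The inputs below are assumptions, varied to show the range.

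**Notation.** *d* = share of patients who leave for good; *K* = appointments in the window for a patient who stays; *s* = visits made by a leaver before leaving; *a* = share of visits made on time.

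**1. Table 11 layout (visits only).** If leavers and stayers are equally punctual while attending:

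measure = [(1−d)·K·a + d·s·a] / [(1−d)·K + d·s] = a

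The result does not depend on *d*. With a = 100% it is 100% at any drop-out rate; with a = 90% it is 90%. Cutting *d* from 30% to 10% moves it by 0 points.

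**2. One miss counted per leaver.** This applies if each appointment is booked at the previous visit and the last, unkept one is counted. The SAP states neither. Stayers keep everything (a = 100%).

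- Pooled appointments, K = 18, leavers keep 3 and miss 1: [(1−d)·18 + 3d] / [(1−d)·18 + 4d].
  - d = 30%: 13.5/13.8 = 97.8%
  - d = 10%: 16.5/16.6 = 99.4%
  - Change: 1.6 points
- Pooled, K = 6, leavers keep 1 and miss 1: [(1−d)·6 + d] / [(1−d)·6 + 2d].
  - d = 30%: 4.5/4.8 = 93.8%
  - d = 10%: 5.5/5.6 = 98.2%
  - Change: 4.5 points
- Averaged per patient, leavers at 3/4: (1−d) + 0.75d.
  - d = 30%: 92.5%
  - d = 10%: 97.5%
  - Change: 5.0 points
- Averaged per patient, leavers at 1/2: (1−d) + 0.5d.
  - d = 30%: 85.0%
  - d = 10%: 95.0%
  - Change: 10.0 points

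The true change in the share still in care is 70% to 90%, or 20 points, each time. The SAP does not say whether appointments are pooled or averaged per patient, so none of these is excluded. They are illustrations, not bounds.

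**3. Level of overstatement.** Take K = 18, leavers stopping after 6 visits, a = 100%, pooled. Compare one miss counted, [(1−d)·18 + 6d] / [(1−d)·18 + 7d], with every appointment due to the end of the window, [(1−d)·18 + 6d] / 18.

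| d | One miss | All due | Still in care |
|---|---|---|---|
| 10% | 99.4% | 93.3% | 90% |
| 20% | 98.7% | 86.7% | 80% |
| 30% | 98.0% | 80.0% | 70% |
| 50% | 96.0% | 66.7% | 50% |

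Against all appointments due, the excess runs from 6.1 points (99.4 − 93.3) to 29.3 points (96.0 − 66.7).

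**4. Windows.** Section 5.8 gives around 18 months of link data. Table 11 has 4 periods of 5 months, or 20. Sections 4.3 and 6.5 give 21. The window decides which appointments count, so these must agree.

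**The case against.** The strongest reply is that the 5.5 sentence gives its own ground, the cross-sectional survey, and that the rest of 5.5 is about household call-backs and missing survey variables. Read in place, it is a loosely worded survey sentence, and 6.5 openly treats other data as longitudinal. This is fair: taken alone, the sentence needs only an editorial correction. It does not supply the missing rule for outcome f.

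A second reply is that the SAP openly defines outcome f as appointments kept, so replacing it is a matter of preference. The SAP is dated 6 April 2016, after the follow-up survey of September to November 2015, and section 1.4 says nothing changes from the protocol. This also stands in part. It argues for keeping the stated measure, relabelled, and adding another beside it.

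Several stronger readings are tempting but not supported:

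- That a leaver counts as exactly one missed appointment. The SAP does not say how appointments are booked. Table 11 implies none; several booked in advance would give more.
- That any lateness is penalised. Visits within 3 days count as attended.
- That a move to another trial clinic looks like a lapse. Table 11 tabulates visits, so they would appear under the new clinic, and 5.8 covers all eight.
- That refill adherence is overstated too. Section 7.1 says only "Adherence will be defined by using the records of pharmacy refills" and gives no denominator, so overstatement there is not shown.
- That the primary objective cannot be answered. Section 2.1.1 names access, adherence and management, not retention.

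**Conclusion.** The point holds for outcome f. As laid out, it describes punctuality among those who attend, overstates retention in each arm wherever patients leave, and is insensitive to a real change in leaving. For a fall in permanent drop-out from 30% to 10%, the response is 0 points on the Table 11 layout. It is about 1.6 to 5 points if one miss is counted, or 10 with few appointments, early leaving and per-patient averaging. The size therefore rests on assumed appointment frequency, time of leaving and averaging; the 0 also assumes that leavers and stayers are equally punctual while attending. In all these scenarios the measure moves by at most half of the true 20 points.

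A reader might infer that the comparison is biased towards one arm. The documents do not settle that: it depends on whether leaving differs by arm. Outcome e, a population proportion, counts a non-attender as not attending and does not share the problem. The survey outcomes and the primary outcome are untouched. This should be corrected, but it concerns one secondary outcome.

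**What to change.** 1. Limit the 5.5 sentence to the two surveys, and state how clinic-link patients who stop attending, die, move away, change clinic or withdraw consent are handled.
2. Keep appointments kept as outcome f, but use appointments due as its denominator, including those with no later visit. Say whether they are pooled or averaged per patient, describe the result as appointment-keeping, and change Table 11 to match. This alone may add only about one miss per leaver, so step 3 is still needed.
3. Add a patient-level retention measure, labelled as added after data collection and declared in 1.4: among hypertensive patients first recorded in the first period, the proportion with a visit at any of the eight clinics in the last complete period, analysed by arm of first clinic. Remove patients whom the census records as dead or out-migrated before that period, and report their numbers by arm.
4. Reconcile the 18-, 20- and 21-month windows.

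The cost is SAP wording and re-analysis of linked visit and census data already held. Two things need checking: that the date of an appointment with no later visit is stored, which the SAP does not say, and that the census, updated yearly (section 3.2), covers the last period. Patients first recorded later are left out of the added measure. Its cohort is defined by attendance and consent after randomisation, so it can only be supportive.
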